5.2.1.8. Prior Biologic Mechanism of Actions

Anti-tumor necrosis factor-alpha therapies:

- Adalimumab
- Golimumab
- Infliximab

Anti-integrin therapy:

- Vedolizumab

Anti-interleukin-12 and interleukin-23 therapy

- Ustekinumab

5.2.1.9. Creatinine Clearance

Creatinine clearance (mL/min) will be estimated using the Cockcroft-Gault equation, as follows:

$$\text{Estimated creatinine clearance (mL/min)} = \frac{(140 - \text{Age}) \times \text{Ideal Body Weight (kg)}}{72 \times \text{Serum Creatinine (mg/dL)}} \text{, if male}$$

$$\frac{(140 - \text{Age}) \times \text{Ideal Body Weight (kg)}}{72 \times \text{Serum Creatinine (mg/dL)}} \times 0.85 \text{, if female}$$

Ideal body weight =	50 kg + 2.3 kg for each 2.54 cm over 152.4 cm	, if male
Ideal body weight =	45.5 kg + 2.3 kg for each 2.54 cm over 152.4 cm	, if female
Serum Creatinine (mg/dL) =	Serum Creatinine (umol/L)/88.4	

5.2.2. Missing Date Imputation

5.2.2.1. Missing/Incomplete AE/Start Date

Imputation of dates with missing day and/or month is only applied to TEAEs. TEAE start dates with missing day or month will be imputed as follows:

- If day and month are missing but year is available, then the imputed day and month will be 01 Jan or the initial treatment date if they have the same year, whichever is later (because TEAE onset is not expected prior to administration of study treatment)
- If day is missing but the month and year are available, then the imputed day will be the first day of the month or the initial injection date if they have the same month and year, whichever is later.

5.2.2.2. Missing/Incomplete AE/Medication End Date/Time

Imputation of dates with missing day and/or month is only applied to TEAEs when AE duration is calculated. TEAE end dates with missing day or month will be imputed as following:

- If day and month are missing but year is available, then the imputed day and month will be 31 Dec [with a time of 23:59 if applicable] or the study exit date if they have the same year, whichever is earlier
- If day is missing but the month and year are available, then the imputed day will be the last day of the month or the study exit date if they have the same month and year, whichever is earlier.

5.2.2.3. Missing/Incomplete Start for Medication

To determine whether medications were used prior to initiation of dosing and whether they were used after initiation of dosing, missing or partial dates for medications will be imputed according to the following rule:

Missing medication start date/time:

- If day and month are missing but year is available, then the imputed day and month will be 31 Dec [with a time of 23:59 if applicable] or the study exit date if they have the same year, whichever is earlier.
- If day is missing but the month and year are available, then the imputed day will be the first day [or 1 minute after midnight if applicable] of the month or the first dose date if they have the same month and year, whichever is later.
- If day, month and years are completely missing, impute as date and time of first dose if 1) end date is not missing and occurs on and after date of first dose, or 2) end date is missing but marked as “ongoing”.

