3.2.5. Prior/Concomitant Medications

Prior medications include all medications taken prior to the first dose of study drug, regardless of when they were stopped. Concomitant medications include all non-study medications that the subject was taking prior to the Day 1 visit that were ongoing at the visit, in addition to all medications with a start date on or after the first dose date and no later than the last dose date + 28 days. Medications with a start date after the last dose date + 28 days will not be included in summaries but will be included in the listing of concomitant medications, with a flag.

Recorded prior and concomitant medication names from the Prior and Concomitant Medications eCRF page will be mapped according to the [REDACTED]

Prior and concomitant medication use will be tabulated separately. Medications that stopped more than 60 days prior to screening will not be included in the prior medication summaries. The number and percentage of subjects who have taken each medication will be provided by study treatment.

On-going Ulcerative Colitis Medications of Interest at Baseline will also be presented. Ulcerative Colitis Medications of Interest include aminosalicylates and corticosteroids. Should a subject enter the study on prohibited biologics and immunomodulators these medications will also be presented.

On-treatment rescue medication use will be summarized. Rescue medications are medications to treat UC or AE of worsening UC and are categorized as :

- Initiation of oral corticosteroids or aminosalicylates

- Increase in oral corticosteroids or aminosalicylates dose above baseline
- Prohibited medications

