5.2.2.3. Missing/Incomplete Start for Medication

To determine whether medications were used prior to initiation of dosing and whether they were used after initiation of dosing, missing or partial dates for medications will be imputed according to the following rule:

Missing medication start date/time:

- If day and month are missing but year is available, then the imputed day and month will be 1 Jan [with a time of 01-01T00:01 if applicable] or the study exit date if they have the same year, whichever is earlier.
- If day is missing but the month and year are available, then the imputed day will be the first day [or 1 minute after midnight if applicable] of the month or the first dose date if they have the same month and year, whichever is later.
- If day, month and years are completely missing, impute as date and time of first dose if 1) end date is not missing and occurs on and after date of first dose, or 2) end date is missing but marked as “ongoing”.

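### The Phase 2b SAP dates year-only medication starts with an end-date rule, so a drug begun before first dose in the same calendar year is dated on or after first dose (minor)

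*SAP*

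**What the plan says.** Section 5.2.2.3 of the Phase 2b SAP states its own purpose: "To determine whether medications were used prior to initiation of dosing and whether they were used after initiation of dosing". It has three bullets.

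- Year known only: "then the imputed day and month will be 31 Dec [with a time of 23:59 if applicable] or the study exit date", the exit date applying when it falls in the same year, and the earlier of the two being used.
- Month and year known: the first day "of the month or the first dose date if they have the same month and year, whichever is later".
- Nothing known: the first dose date, provided the drug ended on or after first dose or is marked as ongoing.

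Three other rules can be set beside the first bullet.

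- Phase 2b SAP 5.2.2.2, on end dates, opens with "TEAE end dates with missing day or month will be imputed as following". Its year-only bullet gives the same 31 December or study exit rule.
- Phase 2b SAP 5.2.2.1, on adverse event starts: "then the imputed day and month will be 01 Jan or the initial treatment date if they have the same year, whichever is later".
- Maintenance SAP 5.2.2.3, on the same medication field: "then the imputed day and month will be 1 Jan [with a time of 01-01T00:01 if applicable"], or study exit if earlier in the same year.

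The dates feed Phase 2b SAP 3.2.5. Prior medications are those taken before first dose. Concomitant medications are those ongoing at Day 1, "in addition to all medications with a start date on or after the first dose date" and no later than 28 days after last dose. A drug with a later start "will not be included in summaries but will be included in the listing of concomitant medications, with a flag".

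Protocol 6.4.1.2 accepts a year alone as the minimum for start and stop dates in the medication history, so year-only records are expected.

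**The concern.** A rule that moves an unknown date as late as possible suits an end date, because it avoids cutting use short. Applied to a start date it does the reverse: it can move the start past the first dose, and past the drug's own stop date. The classification that section 5.2.2.3 is meant to support then fails for every drug begun before dosing in the calendar year of first dose and dated by year alone.

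The medication tables are directly at stake. Further off is intercurrent event 4 in SAP 3.3.4.1, the start of an oral corticosteroid or aminosalicylate not ongoing at baseline. A false event of that kind would set the subject to non-remission in the key secondary analysis and to zero change in Supplementary Estimand 1. The summary of on-treatment rescue medication in SAP 3.2.5 also counts initiations of these drugs.

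**Working it through.** **Notation.** F is the first dose date, E the study exit date, Y the recorded year of the start, S the imputed start.

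**Rule as written.** S = min(31 Dec Y, E) if E falls in Y; otherwise S = 31 Dec Y.

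**Y is the year of F.** Both 31 December of Y and E are on or after F, so S ≥ F always. The true start before F is never recovered.

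**Enumeration.** Each rule was run for every first-dose date of a 365-day year, with assumed intervals from first dose to exit of 14, 56, 84, 140 and 476 days. The counts were the same at all five intervals.

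| Rule | S before F | S on F | S after F |
|---|---|---|---|
| Phase 2b medication start | 0 | 1 | 364 |
| Maintenance medication start | 364 | 1 | 0 |
| Phase 2b adverse event start | 0 | 365 | 0 |

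In a 366-day year the first row is 0, 1 and 365.

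**Y is the year before F.** The latest possible S is 31 December of that year, which precedes F. Misdated: 0 of 366 first-dose dates.

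**Example.** First dose 16 March 2020, start recorded as 2020. With exit on 8 June 2020 the Phase 2b rule gives 8 June 2020; with exit on 1 March 2021 it gives 31 December 2020. The Maintenance rule gives 1 January 2020 in both cases.

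**Stop dates.** If the drug stopped before F, then stop < F ≤ S, so the imputed start is later than the recorded stop. Section 5.2.2.3 has no check for this.

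**Effect on the tables, on dates alone.**

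- Drug ongoing at Day 1: already concomitant under SAP 3.2.5. It loses its prior entry and looks newly started.
- Drug stopped before first dose: misclassified as concomitant.
- S more than 28 days after last dose: left out of the summaries and only listed. This can happen. Protocol Table 1 puts the End of Study visit 4 weeks after last dose with a window of -3 to +5 days, so exit falls at 28 - 3 = 25 to 28 + 5 = 33 days. An exit at 29 to 33 days, used as S, exceeds the limit. This applies to subjects who leave through that visit; the SAP does not define a study exit date for those who roll into Maintenance.

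**Intercurrent event 4.** The event must precede Week 8. For a subject with exit at Day 56 or later, 31 December falls within 56 days counting from first dose only if F is in the last 56 days of the year: 56 of 365 dates. The drug must also be an oral corticosteroid or aminosalicylate, dated only to the first-dose year, and not recorded as ongoing at baseline. The documents give no count of such records, so no frequency follows.

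**The case against.** The other side has several fair points.

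- **Landing on first dose is not peculiar to this bullet.** The other two bullets of 5.2.2.3 can do it, and so does the adverse event rule in 5.2.2.1. This stands. What is peculiar to the year-only bullet is that it goes past first dose.
- **Few records may be affected.** The year-only minimum is stated for medication history; Protocol 6.4.1.12 asks for start and stop dates of concomitant drugs without that allowance. Eligibility also requires recent, stable timing for steroids and aminosalicylates. This limits the size but does not make the rule right.
- **The SAP introduction says the appendices are not a formal section of the signed SAP.** True, but the visible text gives no other rule for partial medication start dates, so a programmer would follow this one. Parts of the appendix are redacted.
- **1 January could hide a true on-study start.** This stands as a cost. The alternative of 1 January or first dose, whichever is later, would put all 365 cases on first dose and still never show use before dosing.

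A reader might infer that the error biases the key secondary result. The documents do not support that. Event 4 requires that the drug was not ongoing at baseline, and SAP 3.2.2 records corticosteroid and aminosalicylate use at enrolment. The exposed case is mainly a drug stopped before first dose. A reader might also infer that every affected drug moves from the prior to the concomitant table; a drug ongoing at Day 1 belongs in both and loses only its prior entry.

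**Conclusion.** Wrong as written, and minor. The misdating is certain for every pre-dose start dated only to the calendar year of first dose, and absent for starts in earlier years. It rests on no assumption beyond study exit not preceding first dose. The consequence is wrong classification in the medication summaries, with some drugs dropped to the listing. A false rescue initiation or intercurrent event 4 is possible but unlikely, and its frequency cannot be derived from the documents. The primary analysis of change in total Mayo score follows a treatment-policy strategy, uses data as collected after such events, and is not affected.

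**What to change.** Change the year-only bullet of Phase 2b SAP 5.2.2.3 to 1 January of the recorded year, consistent with the Maintenance SAP. No cap at the stop date is needed, because 1 January of the start year cannot follow a valid stop date. State that, for intercurrent event 4, use at baseline is taken from the recorded baseline data and not from imputed dates. List oral corticosteroid and aminosalicylate starts dated only to the first-dose year for blinded review before database lock.

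The cost is one line of text and code, one sentence on event 4, and a short listing. The downside is that a true on-study start known only by year would be classed as pre-dose unless the listing review catches it. The Maintenance SAP introduction already reports the Phase 2b outcome, so the tables may exist; a count of affected records would then show whether anything needs rerunning.

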5.2.3. Laboratory Data

For non-efficacy laboratory data, a missing baseline value will be replaced with the last available assessment, generally the screening assessment. A retest value will be used if the original test result is invalid, e.g., specimen hemolyzed.

Laboratory data that are continuous in nature but are less than the lower limit of quantitation/limit of detection (LOD) will be, in general, imputed as follows:

- A value that is 1 unit less than the LOD will be used for calculation of descriptive statistics if the data are reported in the form of “< x” (x is considered as the LOD). More specifically, $x-1$ is used for data summarization if the data are reported in the form of “< x”; and $x.e$ where $e = d-1$, will be used for analysis if the data are reported in the form of “< x.d”; Note:

Laboratory data that are continuous in nature and above the upper limit of quantitation/limit of detection (LOD) will be, in general, imputed as follows:

- A value that is 1 unit more than the LOD will be used for calculation of descriptive statistics if the data are reported in the form of “> x” (x is considered as the LOD). More specifically, $x+1$ is used for data summarization if the data are reported in the form of “> x”; and $x.e$ where $e = d+1$, will be used for analysis if the data are reported in the form of “> x.d”;

5.2.4. AE Severity

Instructions:

- AE severity should be provided through data cleaning process as much as possible. If AE severity is not available because a subject was lost to follow-up, sample text for the data imputation is provided below.

For graded adverse event summaries, AEs with no grade reported will be graded as severe.

5.3. Adverse Event Start and End Date/Time Imputation Rules

Missing start date and times will be handled as follows:

- AE onset date completely missing:
 - If AE is not ongoing and AE onset date missing and AE end date missing, then impute AE onset as date/time of first dose.
 - Else if AE is not ongoing and AE onset date missing and AE end date not missing and date/time of first dose \leq AE end date, then impute AE onset as date/time of first dose of study drug.
 - Else if AE is not ongoing and AE onset date missing and AE end date not missing and AE end date is BEFORE first dose of study drug, then impute AE onset as AE end date YEAR and MONTH with 01 as the day and 00:00 as time.
 - Else if AE IS ongoing and AE onset date missing, then impute AE onset as date/time of first study drug dose.
- AE onset date has year and month only:
 - If AE onset date has year and month only and they are the year and month of first dose of study drug, then impute AE onset as date/time of first dose:
 - Else if AE onset date has year and month only and date/time of first dose is not missing, then impute AE onset as AE onset year and month with 01 as the date and 00:00 as the time.
- AE onset date has year only:
 - If AE onset date has year only and it is year of first dose of study drug, then impute AE onset as date/time of first dose of study drug.
 - Else if AE onset date has year only and date of first study drug dose is not missing and year of AE onset is NOT the year of first dose of study drug, then impute AE onset as Jan. 1 of the AE onset year and 00:00 as the time.
- AE onset missing (where it was not handled by the above cases):
 - If AE onset date is missing, then impute AE onset as date/time of first study drug dose.
- AE onset has complete date but missing time:
 - If AE onset date is a date only and is same as date of first study drug dose, then impute AE onset as date/time of first study drug dose:
 - Else if AE onset date is a date only and is NOT = date of first study drug dose, then impute AE onset as AE onset date with 00:00 as the time:

Missing end date and times will be handled as follows:

- AE end date - completely missing:

- If AE is not ongoing and both AE onset and AE end dates are missing, then impute AE end date as date/time of last study drug dose.
 - Else if AE is not ongoing and AE onset date not missing and AE end date missing AND AE onset date \leq date/time of last dose, then impute AE end date as date/time of last study drug dose.
 - Else if AE is not ongoing and AE onset date is not missing and AE end date is missing and date of last dose is not missing and AE onset is AFTER date of last dose, then impute AE end date as the last day of the month of AE onset date, with 23:59 as time.
- AE end date = year and month only:
 - If AE is NOT ongoing and AE end date consists of year and month only, then impute AE end date as the last day of the month of AE end date month and year, with 23:59 as time.
 - AE end date = year only:
 - If AE is NOT ongoing and AE end date consists of a year only, and year = year of AE onset and AE onset date \leq date of last study drug dose, then impute AE end date as the date of last study drug dose.
 - Else if AE is NOT ongoing and AE end date consists of a year only, and year = year of AE onset and AE onset date $>$ date of last study drug dose, then impute AE end date as the year and month of AE onset, with the last day of the month as the day, and 23:59 as the time.
 - AE end date = complete date but no time:

If AE is NOT ongoing and AE end date consists of a complete date but no time, then impute AE end date = trim(AE end date) || "T23:59".

5.4. Diary Data derivations

5.4.1. Selection of diary days to use in calculation

Derivation of rectal bleeding and stool frequency subscores will consider the 7 days prior to:

- Treatment start date for calculation Baseline score.
- Start date of study visit for Week 2, 4, 8a, 12 and 16.

Days of endoscopy prep, days of endoscopy and the day after endoscopy are set to missing as endoscopy affects rectal bleeding (and stool frequency)

To select the appropriate 3 days in the calculation:

- Find 3 most recent consecutive days in 7 day period
- If 3 days of consecutive diary data are not available then use 3 most recent days
- If there are not 3 days of data available then missing

5.4.2. Rectal Bleeding

Score calculated by averaging the 3 days and rounding to closest whole number i.e. scores of 1, 2, 2, then average= 1.67, round to score of 2

5.4.3. Stool Frequency

Score calculated through the following steps:

- Average stool score calculated by taking average of the 3 days selected scores and rounding to closest whole number (from Evening Diary)
- Average stool score then has the subjects normal stool count subtracted (from Normal Stool Frequency) from it to give number of stools above normal
- Then this new score (number of stools above normal) is mapped as follows

5.4.4. Diary Weeks

Analysis of endpoints by diary weeks will be mapped according to the table below:

Table 11: Diary Weeks

Nominal Period	Start (days)	Stop (days)
Diary Week 1	1	7
Diary Week 2	8	14
Diary Week 3	15	21
Diary Week 4	22	28
Diary Week 5	29	35
Diary Week 6	36	42
Diary Week 7	43	49
Diary Week 8	50	56
Diary Week 9	57	63
Diary Week 10	64	70
Diary Week 11	71	77
Diary Week 12	78	84
Diary Week 13	85	91
Diary Week 14	92	98
Diary Week 15	99	105
Diary Week 16	106	112

[REDACTED]

[REDACTED]

[REDACTED]

[REDACTED]

[REDACTED]

[REDACTED]

[REDACTED]

[figure not shown]
[REDACTED]

[REDACTED]

[figure not shown]
[REDACTED]

[figure not shown]
[REDACTED]

[REDACTED]

■ [Redacted]

[Redacted text block]

[Redacted text block]

[Redacted text block]

[Redacted line]

[Redacted line]

[Redacted line]

[figure not shown]
[Redacted line]

[Redacted line]

[figure not shown]
[Redacted line]

[figure not shown]
[Redacted line]

[Large redacted block]

5.8. CTCAE Grading

Grading Criteria for Clinical Laboratory Tests [CTCAE Version 5.0]					
Hematology Tests		Criteria			
Test	Direction	1	2	3	4
Hemoglobin (g/L)	Decrease	≥ 100 - <LLN	≥ 80 - <100.0	≥ 65 - <80	<65
Leukocytes (WBC) ($10^9/L$)	Decrease	≥ 3.0 - <LLN	≥ 2.0 - <3.0	≥ 1.0 - <2.0	<1.0
Lymphocytes ($10^9/L$)	Decrease	≥ 0.8 - <LLN	≥ 0.5 - <0.8	≥ 0.2 - <0.5	<0.2
Neutrophils ($10^9/L$)	Decrease	≥ 1.5 - <LLN	≥ 1.0 - <1.5	≥ 0.5 - <1.0	<0.5
Platelets ($10^9/L$)	Decrease	≥ 75.0 - <LLN	≥ 50.0 - <75.0	≥ 25.0 - <50.0	<25.0
Chemistry Tests		Criteria			
Test	Direction	1	2	3	4
ALT	Increase	>ULN - ≤ 3.0 Xuan if baseline was normal; 1.5 - 3.0 x baseline if baseline was abnormal	>3.0 xULN - ≤ 5.0 xULN if baseline was normal; >3.0 - 5.0 x baseline if baseline was abnormal	>5.0 xULN - ≤ 20.0 xULN if baseline was normal; >5.0 - 20.0 x baseline if baseline was abnormal	>20.0 xULN if baseline was normal; >20.0 x baseline if baseline was abnormal
Albumin (g/L)	Decrease	≥ 30 - <LLN	≥ 20 - <30	<20	
Alkaline Phosphatase	Increase	>ULN - ≤ 2.5 xULN if baseline was normal; 2.0 - 2.5 x baseline if baseline was abnormal	>2.5 xULN - ≤ 5.0 xULN if baseline was normal; >2.5 - 5.0 x baseline if baseline was abnormal	>5.0 xULN - ≤ 20.0 xULN if baseline was normal; >5.0 - 20.0 x baseline if baseline was abnormal	>20.0 xULN if baseline was normal; >20.0 x baseline if baseline was abnormal
AST	Increase	>ULN - ≤ 3.0 xULN if baseline was normal; 1.5 - 3.0 x baseline if baseline was abnormal	>3.0 xULN - ≤ 5.0 xULN if baseline was normal; >3.0 - 5.0 x baseline if baseline was abnormal	>5.0 xULN - ≤ 20.0 xULN if baseline was normal; >5.0 - 20.0 x baseline if baseline was abnormal	>20.0 xULN if baseline was normal; >20.0 x baseline if baseline was abnormal
Bilirubin	Increase	>ULN - ≤ 1.5 xULN if baseline was normal; > 1.0 - 1.5 x baseline if baseline was abnormal	>1.5 xULN - ≤ 3.0 xULN if baseline was normal; >1.5 - 3.0 x baseline if baseline was abnormal	>3.0 xULN - ≤ 10.0 xULN if baseline was normal; >3.0 - 10.0 x baseline if baseline was abnormal	>10.0 xULN if baseline was normal; >10.0 x baseline if baseline was abnormal
Calcium (mmol/L)	Increase	>ULN - ≤ 2.9	>2.9 - ≤ 3.1	>3.1 - ≤ 3.4	>3.4

Calcium (mmol/L)	Decrease	[Albumin \geq 40 g/L or missing and calcium \geq 2.0 - <LLN]; or [Albumin < 40 g/L and (calcium - 0.8 x (albumin - 40)) \geq 2.0 - <LLN]	[Albumin \geq 40 g/L or missing and calcium \geq 1.75 - <2.0]; or [Albumin < 40 g/L and (calcium - 0.8 x (albumin - 40)) \geq 1.75 - <2.0]	[Albumin \geq 40 g/L or missing and calcium \geq 1.5 - <1.75]; or [Albumin < 40 g/L and (calcium - 0.8 x (albumin - 40)) \geq 1.5 - <1.75]	[Albumin \geq 40 g/L or missing and calcium <1.5]; or [Albumin < 40 g/L and (calcium - 0.8 x (albumin - 40)) <1.5]
Creatine Kinase	Increase	>ULN - \leq 2.5 xULN	>2.5 xULN - \leq 5.0 xULN	>5.0 xULN - \leq 10.0 xULN	>10.0 xULN
Creatinine	Increase	>ULN - \leq 1.5 xULN	>1.5 xULN - \leq 3.0 xULN	>3.0 xULN - \leq 6.0 xULN	>6.0 xULN
GGT	Increase	>ULN - 2.5 x ULN if baseline was normal; 2.0 - 2.5 x baseline if baseline was abnormal	>2.5 - 5.0 x ULN if baseline was normal; >2.5 - 5.0 x baseline if baseline was abnormal	>5.0 - 20.0 x ULN if baseline was normal; >5.0 - 20.0 x baseline if baseline was abnormal	>20.0 x ULN if baseline was normal; >20.0 x baseline if baseline was abnormal
Phosphate (mmol/L)	Decrease	\geq 0.8 - <LLN	\geq 0.6 - <0.8	\geq 0.3 - <0.6	<0.3
Potassium (mmol/L)	Increase	>ULN - \leq 5.5	>5.5 - \leq 6.0	>6.0 - \leq 7.0	>7.0
Potassium (mmol/L)	Decrease	\geq 3.0 - <LLN		\geq 2.5 - <3.0	<2.5
Sodium (mmol/L)	Increase	>ULN - \leq 150	>150 - \leq 155	>155 - \leq 160	>160
Sodium (mmol/L)	Decrease	\geq 130 - <LLN		125-129 mmol/L symptomatic; 120-124 mmol/L regardless of symptoms	<120
Triglycerides (mmol/L)	Increase	1.71 - \leq 3.42	>3.42 - \leq 5.7	>5.7 - \leq 11.4	>11.4

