1. INTRODUCTION

This document outlines the plan for the summarization and analysis of clinical data collected in the Phase 2b Induction Study of Protocol 0157 for TD-1473.

Protocol 0157 comprises 3 separate studies within a single protocol. The purpose of multiple studies within a single protocol is to increase operational efficiency and reduce operational costs.

The analyses and summarization of clinical data is divided into 3 separate SAPs corresponding to the separate studies within the protocol:

- Phase 2b Dose-Finding Induction SAP (this document)
- Phase 3 Dose-Confirming Induction SAP
- Phase 3 Maintenance SAP

Each study set of analyses will control Type I error < 0.05 . As such, study analyses (Phase 2b Induction Study, Phase 3 Induction Study, Phase 3 Maintenance Study) are considered independent and no control of multiplicity will occur across the 3 sets of analyses.

The analysis of pharmacokinetics data (derivation and summarization of individual PK parameters) is outside the scope of this document and is not addressed here.

This document describes the a priori plan for analysis. Any substantive modification to this analysis plan will be identified in the clinical study report (CSR).

Information in the appendices to the SAP are not considered a formal section of the signed SAP.

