3.7.3. Additional Safety Assessments

3.7.3.1. Clinical Laboratory Parameters

Laboratory data, hematology, serum chemistry and urinalysis, will be summarized in terms of observed values and changes from baseline for induction period and overall. In addition, changes from baseline relative to normal ranges from the central lab (e.g., shifts from normal to abnormal high/low) will be summarized.

Summaries for laboratory parameters of special interest will also be presented, these will include:

- Neutrophils
- Leukoocytes
- Lymphocytes
- Hemoglobin
- Lipids [LDL cholesterol, HDL cholesterol, Cholesterol, and Triglyceride]
- Liver Function Test's [ALT, AST, Bilirubin]
- Creatinine
- Creatinine Kinase

The number and percentage of subjects with clinically abnormal lab values will also be summarized by timepoint for the following criteria:

- absolute neutrophil count of $< 1.0 \times 10^9/L$
- white blood cell count of $< 2.0 \times 10^9/L$
- absolute lymphocyte count of $< 0.5 \times 10^9/L$

A summary of maximum National Cancer Institute Common Terminology Criteria for Adverse Events (NCI-CTCAE) toxicity grade (Appendix 5.8) for postbaseline laboratory values through Week 8 and through Week 16.

Listings will flag laboratory values that are outside of normal range.

A listing of all abnormal lab values will be provided. Listings of subjects with any abnormal postbaseline laboratory values of CTCAE grade ≥ 2 will also be provided.

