3.7.3. Additional Safety Assessments

3.7.3.1. Clinical Laboratory Parameters

Laboratory data, hematology, serum chemistry and urinalysis, will be summarized in terms of observed values and changes from baseline. In addition, changes from baseline relative to normal ranges from the central lab (e.g., shifts from normal to abnormal high/low) will be summarized.

The number and percentage of subjects with clinically abnormal lab values will also be summarized by timepoint for the following criteria:

- absolute neutrophil count of $< 1.0 \times 10^9/L$
- white blood cell count of $< 2.0 \times 10^9/L$
- absolute lymphocyte count of $< 0.5 \times 10^9/L$

A summary of maximum National Cancer Institute Common Terminology Criteria for Adverse Events (NCI-CTCAE) toxicity grade (Appendix 5.3) for postbaseline laboratory values.

A listing of all abnormal lab values will be provided.

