Calcium (mmol/L)	Decrease	[Albumin ≥40 g/L or missing and calcium ≥2.0 - <LLN]; or [Albumin < 40 g/L and (calcium - 0.8 x (albumin - 40)) ≥2.0 - <LLN]	[Albumin ≥40 g/L or missing and calcium ≥1.75 - <2.0]; or [Albumin < 40 g/L and (calcium - 0.8 x (albumin - 40)) ≥1.75 - <2.0]	[Albumin ≥40 g/L or missing and calcium ≥1.5 - <1.75]; or [Albumin < 40 g/L and (calcium - 0.8 x (albumin - 40)) ≥1.5 - <1.75]	[Albumin ≥40 g/L or missing and calcium <1.5]; or [Albumin < 40 g/L and (calcium - 0.8 x (albumin - 40)) <1.5]

Creatine Kinase	Increase	>ULN - ≤2.5 xULN	>2.5 xULN - ≤5.0 xULN	>5.0 xULN - ≤10.0 xULN	>10.0 xULN
Creatinine	Increase	>ULN - ≤1.5 xULN	>1.5 xULN - ≤3.0 xULN	>3.0 xULN - ≤6.0 xULN	>6.0 xULN
GGT	Increase	>ULN - 2.5 x ULN if baseline was normal; 2.0 - 2.5 x baseline if baseline was abnormal	>2.5 - 5.0 x ULN if baseline was normal; >2.5 - 5.0 x baseline if baseline was abnormal	>5.0 - 20.0 x ULN if baseline was normal; >5.0 - 20.0 x baseline if baseline was abnormal	>20.0 x ULN if baseline was normal; >20.0 x baseline if baseline was abnormal
Phosphate (mmol/L)	Decrease	≥0.8 - <LLN	≥0.6 - <0.8	≥0.3 - <0.6	<0.3
Potassium (mmol/L)	Increase	>ULN - ≤5.5	>5.5 - ≤6.0	>6.0 - ≤7.0	>7.0
Potassium (mmol/L)	Decrease	≥3.0 - <LLN		≥2.5 - <3.0	<2.5
Sodium (mmol/L)	Increase	>ULN - ≤150	>150 - ≤155	>155 - ≤160	>160
Sodium (mmol/L)	Decrease	≥130 - <LLN		125-129 mmol/L symptomatic; 120-124 mmol/L regardless of symptoms	<120
Triglycerides (mmol/L)	Increase	1.71 - ≤3.42	>3.42 - ≤5.7	>5.7 - ≤11.4	>11.4

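### The low-calcium CTCAE rule in both SAPs adds 0.8 mmol/L for each 1 g/L of albumin below 40, so grade 2 or worse cannot occur at albumin 37.5 g/L or lower

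*SAP*

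**What the plan says.** The grading appendices of the two SAPs (Phase 2b SAP 5.8 and Maintenance SAP 5.3) carry the same low-calcium row. It is headed "Calcium (mmol/L", and albumin is in g/L both inside the rule and in its own row of the table.

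- **Albumin 40 g/L or higher, or missing:** measured calcium is graded directly. The grade 2 cell, for example, reads "or missing and calcium ≥1.75 - <2.0" and the grade 4 cell "or missing and calcium <1.5".
- **Albumin below 40 g/L:** an adjusted value is graded against the same cut-offs. The condition and formula are "Albumin < 40 g/L and (calcium - 0.8 x (albumin - 40", with the closing brackets following. The expression stands in all four grade cells of each SAP.

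The grades feed planned safety outputs. Section 3.7.3.1 of the Phase 2b SAP asks for a maximum-grade summary through Week 8 and through Week 16, and adds: "Listings of subjects with any abnormal postbaseline laboratory values of CTCAE grade ≥ 2 will also be provided". The same section of the Maintenance SAP asks for a summary of maximum "toxicity grade (Appendix 5.3) for postbaseline laboratory values".

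**The concern.** The coefficient does not fit the units. Rearranged, the graded value is calcium + 0.8 × (40 − albumin), so a small albumin shortfall adds an amount comparable with calcium itself. The table's own limits show the problem. It grades albumin down to below 20 g/L, so low albumin is foreseen, and its highest cut-off for raised calcium is 3.4 mmol/L. At albumin 35 g/L the adjustment alone is 4.0 mmol/L, which exceeds that cut-off before any measured calcium is added. This comparison is only a plausibility check: the raised-calcium row has no albumin term, so nobody would be misgraded as high.

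The consequence runs in one direction. Subjects with both low calcium and albumin below 40 g/L can be graded too low or not at all, and below a certain albumin level the grade 2 or higher listing cannot show low calcium for anyone.

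**Working it through.** **Inputs.** Coefficient 0.8, reference albumin 40 g/L, and lower cut-offs 2.0, 1.75 and 1.5 mmol/L, all from the low-calcium rows of the two SAPs. Grade 1 runs from 2.0 up to the lower limit of normal (LLN). The LLN is not stated, so 2.1 to 2.2 mmol/L is assumed where it is needed. The SAPs give no derivation or source for 0.8, so that figure cannot be reproduced.

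**Formula as printed.** Graded value = Ca + 0.8 × (40 − albumin), for albumin below 40.

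**Albumin levels at which a grade becomes impossible.** Measured calcium cannot be negative, so a grade with upper cut-off c cannot occur once 0.8 × (40 − albumin) ≥ c, that is, at albumin ≤ 40 − c/0.8:

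- Grade 4: 40 − 1.5/0.8 = 38.125 g/L
- Grade 3 or worse: 40 − 1.75/0.8 = 37.8125 g/L
- Grade 2 or worse: 40 − 2.0/0.8 = 37.5 g/L
- Any grade: 40 − 2.1/0.8 = 37.375 to 40 − 2.2/0.8 = 37.25 g/L (assumed LLN)

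A grid search over calcium from 0.01 mmol/L upward, in albumin steps of 0.01 g/L, found 37.52 g/L as the lowest albumin that allows any grade 2 or worse. This agrees with the algebra.

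**Measured calcium (mmol/L) below which grade 2 or worse applies:**

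| Albumin (g/L) | Add-on with 0.8 | Limit with 0.8 (2.0 − add-on) | Limit with 0.02 |
|---|---|---|---|
| 39 | 0.8 | 1.20 | 1.98 |
| 38 | 1.6 | 0.40 | 1.96 |
| 37.5 | 2.0 | 0 (impossible) | 1.95 |
| 35 | 4.0 | −2.0 (impossible) | 1.90 |
| 30 | 8.0 | −6.0 (impossible) | 1.80 |
| 20 | 16.0 | −14.0 (impossible) | 1.60 |

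**Where 0.02 comes from.** This is an assumption, because the SAPs do not say where 0.8 originates. If it was meant as mg/dL of calcium per g/dL of albumin, then 0.8 × 0.2495 mmol/L per mg/dL ÷ 10 g/L per g/dL = 0.01996, about 0.02 mmol/L per g/L. The printed value is 0.8/0.02 = 40 times that.

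**Worked examples:**

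| Ca (mmol/L) | Albumin (g/L) | As printed | Unadjusted | With 0.02 |
|---|---|---|---|---|
| 1.4 | 39.5 | 1.4 + 0.4 = 1.8, grade 2 | grade 4 | 1.41, grade 4 |
| 1.4 | 38 | 1.4 + 1.6 = 3.0, no grade | grade 4 | 1.44, grade 4 |
| 1.6 | 35 | 1.6 + 4.0 = 5.6, no grade | grade 3 | 1.70, grade 3 |
| 2.12 | 35 | 2.12 + 4.0 = 6.12, no grade | grade 1 or none, by LLN | 2.22, no grade |

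The last row shows that mild cases can agree. For more marked values the grade disappears close to 40 g/L. Calcium 1.6 is ungraded at albumin ≤ 40 − (2.1 − 1.6)/0.8 = 39.375 (LLN 2.1) or ≤ 40 − (2.2 − 1.6)/0.8 = 39.25 (LLN 2.2). Calcium 1.0 is ungraded at albumin ≤ 38.625 or ≤ 38.5 on the same two assumptions.

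**The case against.** The arithmetic is hard to dispute; the case against is about consequence.

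- **Calcium is a minor parameter here.** It is not among the Phase 2b laboratory parameters of special interest. Nor is it among the clinically abnormal criteria in either SAP, or the laboratory abnormalities named in protocol Section 7.2 (a list that is not closed).
- **Low values are not hidden.** Observed values, changes from baseline, reference-range shifts and listings of abnormal values remain in both SAPs.
- **The outputs are descriptive.** The Maintenance Study ended early and is reported in an abbreviated CSR.
- **The appendix has limited standing.** The Phase 2b SAP Introduction says "Information in the appendices to the SAP are not considered a formal section of the signed SAP".
- **Some upward adjustment is intended.** The unadjusted grade is therefore not automatically the right one.
- **The program may differ from the text.** Neither code nor output is in the documents.

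The first three points stand and limit the importance of the finding, but none of them corrects the grade tables. The fourth carries little weight: Section 3.7.3.1 of each SAP sends the reader to its appendix for grading, so the appendix is the only stated rule, and the Maintenance SAP has no such sentence in its Introduction. The fifth is fair and is why the comparison with 0.02 is shown, but the impossibility limits need no comparator. The sixth stands: what is established is an error in the specification, and an error in the outputs depends on how it was programmed.

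**Conclusion.** The concern holds. As written, the rule under-grades low calcium when albumin is below 40 g/L and makes grade 2 or worse impossible at 37.5 g/L or lower. The 38.125, 37.81 and 37.5 g/L limits follow exactly from the printed rule and need no outside figure. The limits for no grade at all rest on an assumed LLN of 2.1 to 2.2 mmol/L, and the 0.02 comparison rests on an assumed origin of the 0.8.

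The reach is narrow: the maximum-grade summaries in both SAPs and the Phase 2b grade 2 or higher listing. Subjects with albumin of 40 g/L or higher, or missing, are unaffected, as are the efficacy analyses. The documents do not say how often low calcium and low albumin occur together, so the number of misgraded subjects cannot be estimated. This should be corrected, but it does not threaten the trial's conclusions on efficacy.

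**What to change.** In all four low-calcium cells of both grading appendices, replace 0.8 with a coefficient in mmol/L per g/L and state its source. If the sponsor confirms that 0.8 was a mg/dL-per-g/dL coefficient, the adjusted value becomes calcium + 0.02 × (40 − albumin). Then check which coefficient and units the grading program uses. If it follows the printed rule, rerun the maximum-grade summaries for both studies and the Phase 2b listing of grade 2 or higher. The cost is one constant in two appendices and in the program, plus those reruns.
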